dose:	The Phase I starting dose is 20 mg. Phase II: Recommended Phase II Dose (RP2D), based on the MTD determined in Phase I
mode of admin.:	Intravenous (i.v.) infusion on Days 1 and 15 of each 28-day cycle
Comparator products:	Phase II only: BSC per Investigator's choice
mode of admin.:	NA
Duration of treatment:	Patients with clinical benefit, PR or CR after the 4th (or 6th) Cycle will receive repeated cycles until relapse after Complete Response (CR), Partial Response (PR), erythroid response (HI-E), Red Blood Cell transfusion independency or Marrow Complete Response (mCR), Progressive Disease (PD), or unacceptable adverse event(s), in the absence of other withdrawal criteria.

Proprietary confidential information.

© 2019 Boehringer Ingelheim International GmbH or one or more of its affiliated companies. All rights reserved.

This document may not - in full or in part - be passed on, reproduced, published or otherwise used without prior written permission.

Name of company: Boehringer Ingelheim		Tabulated Trial Protocol	
Name of finished product: Not Applicable			
Name of active ingredient: BI 836858			
Protocol date: 06 MAR 2014	Trial number: 1315.7		Revision date: 11 SEP 2019
Criteria for efficacy:		
Primary endpoints (Phase II):
 
 
RBC transfusion independency
 
 
Secondary endpoints (Phase I):
 
 
RBC transfusion independency
 
 
Secondary endpoints (Phase I and II):
 
 
Hematologic improvement neutrophils (HI-N)
 
Hematologic improvement platelets (HI-P)
 
Hematologic improvement erythroid (HI-E)
 
Time to HI-E response
 
Mean hemoglobin increase <math>\geq 1.5</math> g/dL
 
Duration of response (RBC Transfusion Independency, HI-N, HI-P, HI-E or Objective Response)
 
Overall Response (CR, PR and HI)
 
	
Criteria for safety:		
Primary endpoints (Phase I):
 
 
Maximum Tolerated Dose (MTD)
 
Occurrence of Dose Limiting Toxicity (DLT)
 
	

Proprietary confidential information.

© 2019 Boehringer Ingelheim International GmbH or one or more of its affiliated companies. All rights reserved.

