#### Phase I:

In Phase I dose escalation part, patients with low to intermediate-1 risk MDS, who have experienced ESA treatment failure, except for patients who do not qualify for ESA treatment and are refractory to or are not amenable or eligible for approved MDS therapy will be assigned to a dose cohort under investigation. After determination of the MTD/RP2D the same group of patients as for the dose escalation will be enrolled in the first expansion cohort (referred to as “pre-treated” patients). The second expansion cohort will enroll patients with low or intermediate-1 risk MDS with symptomatic anemia, who experienced ESA treatment failure or do not qualify (serum erythropoietin level > 500 U) for ESA treatment and who have not received prior HMA and/or lenalidomide (referred to as “untreated” patients). Treatment failure on ESAs is defined as 1) failure or ceasing to

Proprietary confidential information.

show hematologic response after at least 8 weeks of 40,000 to 60,000 IU/week of erythropoietin (EPO) or equivalent or 2) low chance/response to ESA with endogenous serum EPO>500. It is expected that approximately 50 patients will be enrolled.

The Phase I dose-escalation will be guided by a Bayesian logistic regression model with overdose control (refer to [Section 7](#)). At any time in the trial, it will not be permitted to escalate to a dose which does not fulfil the escalation with overdose control (EWOC) criterion (refer to Section 7). Dose-escalation will be restricted to a maximum of 100% from the previous dose.

For any dose-escalation cohort, at least 3 patients will be required (refer to Section 7). However, in the case that only 2 patients are evaluable and neither has experienced a dose-limiting toxicity within the first cycle (2 administrations – 28 days), then dose-escalation can occur based on these 2 patients. After all patients in a cohort have either experienced a DLT or have been observed for at least one cycle (2 administrations – 28 days) without experiencing a DLT, the Bayesian model will be updated with the newly accumulated data. The overdose risk will then be calculated for each dose, and escalation will be permitted to all doses which fulfil the EWOC criterion and the additional 100% escalation rule.

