Patients who have not completed at least 2 administrations (1 cycle) of BI 836858 due to BI 836858 related toxicity will not be replaced; this will be considered as a DLT. However, patients who have not completed at least 2 administrations (1 cycle) of BI 836858 for reasons other than BI 836858 related toxicity will be replaced.

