##### Phase I:

The dose is planned to be escalated in cohorts at pre-defined dose levels based on a maximum escalation of 100%. The provisional dose levels are 20mg, 40mg, 80mg, 160mg, and 320mg. Intermediate or lower dose levels, depending on the number of DLTs observed in the study, may be investigated if agreed upon between Investigator and Sponsor.

For any dose-escalation cohort, at least 3 patients will be required, but two out of those patients must be evaluable patients to escalate dose in next cohort. The DSB will also recommend the size for the next cohort between three to six patients. However, the final decision on the next cohort size will be made by a mutual decision between the TMM and the Coordinating Investigator (CI). After all patients in a cohort have either experienced a DLT or have been observed for at least one cycle (28 days – 2 administrations) without experiencing a DLT, the BLRM will be updated with the newly accumulated data and the overdose risk will be calculated. Based on the model and on additional information (PK, PD patient profiles), the members of the DSB will reach a joint decision on the next dose level to be investigated.

Proprietary confidential information.

© 2019 Boehringer Ingelheim International GmbH or one or more of its affiliated companies. All rights reserved.

This document may not - in full or in part - be passed on, reproduced, published or otherwise used without prior written permission.

During the cohort dose escalation phase, entry into the initial 20mg dose cohort will be allowed after a minimum of 7 days from the first administration of the first patient, and subsequently between patient 2 and 3. If the cohort expands to 6 patients, the 7-day observation period between the subsequent patients must be followed. For subsequent cohorts, enrollment will be allowed after a minimum of 3 days from the first administration of each patient.

Enrollment into the next dose cohort is allowed after the previous dose cohort is found to be safe for all patients in this cohort (e.g. at least 28 days after the first administration of drug in the last patient entered into the cohort). For the purposes of determining dose escalation, Dose Limiting Toxicities will be assessed based on safety data from Cycle 1 (2 administrations – 28 Days), however DLTs will be monitored beyond Cycle 1 and throughout the trial.

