5.1 PRIMARY ENDPOINTS

The primary endpoints in the Phase I part of the trial are the MTD and the number of patients with dose limiting toxicities (DLTs) during the MTD evaluation period.

Maximum tolerated dose (MTD) and number of patients with DLTs during the MTD evaluation period:

The MTD is defined as the highest dose of BI 836858 with less than 25% risk of the true DLT rate being above 33% during the MTD evaluation period. The other primary endpoint, the number of patients with DLTs during the MTD evaluation period will be used to determine the MTD.

MTD evaluation period:

The MTD evaluation period is defined as the time from the first administration of trial medication to start of the third administration of BI 836858, excluding the day of the third administration of BI 836858. In case the third infusion of BI 836858 is not administered, the evaluation period ends 30 days after the last administration.

In case a patient has not completed the required number of administrations due to BI 836858 related toxicity, he/she will not be replaced and this will be considered as DLT. However, patients who have not completed the required number of administrations of BI 836858 for reasons other than BI 836858 related toxicity will be replaced. Patients who were replaced during the MTD evaluation period will not be considered for MTD evaluation. That is, a patient will be considered evaluable for MTD assessment if he/she received at least 2 administrations of BI 836858 or if he/she received less than 2 administrations due to DLT.

The MTD estimate after the dose escalation part of the trial will be obtained on the basis of DLTs observed during the MTD evaluation period. However, for those patients who receive more than one cycle of the treatment, all AEs that constitute a DLT will be considered in the final determination of the dose recommended for the Phase II part.

As part of this additional analysis the probabilities of the Bayesian 2-parameter logistic regression model with overdose control will be also computed including all considered DLTs.

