6. GENERAL ANALYSIS DEFINITIONS

6.1 TREATMENTS

In the Phase I part, treatments are not randomized (open-label, dose escalation). Different dose levels (planned and intermediate) of the investigational medicinal product will be evaluated. The data will be presented for all dose cohorts separately, in particular, patients will be analysed by the treatment group initially assigned in the first treatment course. In addition, totals over all dose cohorts will be given.

“Analysing treatment periods” will be used for reporting of treatment emergent adverse events (AE) and to differentiate between screening, on-treatment, post-treatment and post-study safety data. The inequalities start date \leq onset date of AE $<$ stop date will determine whether the AE will be assigned to the “analysing treatment period” or not. Table 6.1:1 defines the “analysing treatment periods” which will be used for reporting of treatment emergent AEs and safety laboratory parameters.

Table 6.1:1 Definition of analysing treatment periods

| Analysing treatment period | Start date (including) | Stop date (excluding) |
|----------------------------|---|---|
| Screening | Date of informed consent | Date of first administration of trial medication |
| MTD evaluation period | Date of first administration of trial medication | Date of third infusion or (if the third infusion was not administered) Date of first administration of trial medication + 28 days |
| On-treatment | Date of first administration of trial medication | Start date of ‘Follow-up’ |
| Follow-up | Date of end of REP +1 day, i.e. Date of last administration of trial medication + 30 days of REP + 1 day | Start date of ‘Post-study’ |
| Post-study | Last date patient status obtained / last date patient known to be alive + 1 (if patient is lost to follow-up) / date of refusal + 1 day / the date patient died + 1 | DBL + 1 day |

Data recorded between the first administration of trial medication until up to 30 days (Residual effect period; REP) after the last administration of trial medication will be considered as on-treatment.

In addition, to justify the MTD determination, AEs occurring during the MTD evaluation period will be presented separately from those occurring during the complete on-treatment period.

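### SAP evaluability for the MTD depends on two administrations alone, so a patient lost after Day 15 without a DLT is scored as a first-cycle non-DLT

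*SAP*

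**What the plan says.** SAP 5.1 (Primary endpoints): "a patient will be considered evaluable for MTD assessment if he/she received at least 2 administrations of BI 836858", or fewer than two because of a DLT. No time condition is attached. SAP 6.3 builds the MTD evaluation set from treated patients who were not replaced, citing SAP 5.1 and protocol 3.3.4.1.

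Protocol synopsis: "infusion on Days 1 and 15 of each 28-day cycle".

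Protocol 3.1 (Phase I): the model is updated once all patients in a cohort have had a DLT or "have been observed for at least one cycle (2 administrations – 28 days) without experiencing a DLT". Protocol 4.1.3 repeats it: "observed for at least one cycle (28 days – 2 administrations) without experiencing a DLT".

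Protocol 3.3.4.1 provides for replacement of "patients who have not completed at least 2 administrations (1 cycle) of BI 836858 for reasons other than BI 836858 related toxicity".

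The period in which DLTs count is a separate definition. SAP 5.1 runs it to the "start of the third administration of BI 836858, excluding the day of the third administration of BI 836858"; with no third infusion, "the evaluation period ends 30 days after the last administration". For that same case, SAP Table 6.1:1 gives "Date of first administration of trial medication + 28 days".

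**The concern.** Protocol 7.1 defines the modelled quantity as the probability of a DLT in the first cycle. The binomial likelihood needs that outcome to be known for each patient counted. Under SAP 5.1, someone who receives the Day 15 infusion and leaves observation the next day without a DLT is not replaced and adds one to the denominator and nothing to the numerator. Roughly half the cycle is unobserved, including nearly all the time after the second dose. A haematological DLT that needs more than 7 days of non-recovery (protocol 5.2.1.1) could not then be seen following that dose.

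Scoring an unknown outcome as a non-event lowers the estimated DLT rate and the overdose probability. The MTD is a primary endpoint resting on 21 escalation and 6 expansion patients, so single patients carry weight. The SAP has no rule that would catch the case: missing data are not imputed (6.6), only missing consent leads to exclusion among the listed deviations (Table 6.2:1), and the patient listing in 7.4 shows DLT status and evaluability but not time observed.

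**Working it through.** **Timing.** Second infusion: Day 15. With a third infusion on schedule (Day 29), the window covers Days 1 to 28. Without one, SAP 5.1 ends it at about Day 15 + 30 = Day 45, while Table 6.1:1 (stop date excluded) ends it after Day 28. The two definitions differ by about 45 − 28 = 17 days.

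**Model (protocol 7.1).** logit p(d) = log α + β·log(d/160), with a three-component normal mixture prior on (log α, log β), correlations 0:
- weight 0.90, mean (−2.189, 0.146), SD (2, 1)
- weight 0.05, mean (−0.549, −0.233), SD (2, 1)
- weight 0.05, mean (−4.068, −1.372), SD (5, 0.01)

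Posterior ∝ prior × ∏ p(d)^r · (1 − p(d))^(n − r). P(overdose) is the posterior probability that p(d) ≥ 0.33, and the limit is 0.25. Integration was on a numerical grid.

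**Reproducing the protocol's figures.**
- Table 7.1:2, prior P(overdose) at 20/40/80/160/320 mg: 0.067/0.091/0.136/0.244/0.443 against stated 0.069/0.091/0.138/0.244/0.441.
- Table 10.3:1, scenarios 1 to 9, current dose: 0.009, 0.213, 0.663, 0.004, 0.092, 0.368, 0.282, 0.016, 0.702 against stated 0.010, 0.222, 0.668, 0.004, 0.102, 0.369, 0.289, 0.016, 0.709.

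The largest gap is 0.010 (scenario 5).

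**Removing one DLT-free, under-observed patient.** The DLT counts are assumed, because the documents report none.

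| Constellation | Counted | Not counted | Crosses 0.25? |
|---|---|---|---|
| 20 mg, 1/3 → 1/2 | 0.213 | 0.336 | yes |
| 160 mg, 1/3 → 1/2, after 0/3 at 20, 40, 80 mg | 0.168 | 0.254 | yes, narrowly |
| 320 mg, 1/4 → 1/3, after 0/3 at the four lower doses | 0.176 | 0.264 | yes |
| 80 mg as next dose, after 0/3 at 20 mg and 1/3 → 1/2 at 40 mg | 0.243 | 0.304 | yes, but see below |
| 40 mg, 1/3 → 1/2, after 0/3 at 20 mg | 0.092 | 0.139 | no |
| 80 mg, 1/3 → 1/2, after 0/3 at 20, 40 mg | 0.084 | 0.126 | no |
| 320 mg as next dose, 0/3 → 0/2 at 160 mg, after 0/3 at 20, 40, 80 mg | 0.209 | 0.233 | no |

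The row for 80 mg as next dose is fragile. Scenario 5 of Table 10.3:1 has the same data (0/3, then 1/3) and requires staying at 40 mg, which implies that the sponsor's own value for 80 mg was already at or above 0.25. The 0.243 here is within the reproduction error of that limit. The 20 mg row does not have this problem: the protocol's stated 0.222 for 1/3 is also below 0.25, and 0.336 is well above it.

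If the lost patient had in fact had an unseen DLT, 20 mg would go from 1/3 to 2/3, with P(overdose) 0.213 → 0.663 (stated 0.222 → 0.668).

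**The case against.** A reader might infer that the SAP declares every patient DLT-free on Day 15. It does not. DLT counting runs to the third infusion, or about Day 28 to Day 45 without one. Patients who stop treatment still have an end-of-treatment visit 30 (+7) days after the last dose, and adverse events are collected for 30 days after it (protocol 3.3.4.1, 5.2.2.2, 6.2.3.1). This confines the gap to loss to follow-up, consent withdrawal or death between the Day 15 infusion and the end of the cycle.

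A reader might also infer that the SAP simply departs from the protocol. Protocol 3.3.4.1 is keyed to two administrations as well, and 3.1 and 4.1.3 govern when the model is updated, not who is in the analysis set. That stands: the protocol's passages need reconciling too. But 3.3.4.1 equates two administrations with one cycle, 3.1 and 4.1.3 equate one cycle with 28 days, and SAP 5.1 carries neither equation over.

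Three further points hold:
- A DLT-free replacement would restore 1/3 and its overdose probability. That was possible while recruitment was open; it is not at the final analysis.
- A drug-related delay of Cycle 2 is judged at Day 57, so a 28-day condition does not capture that criterion.
- Exclusion has its own bias: early DLTs are kept while partly observed non-DLTs are dropped.

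The additional model run with all later DLTs (SAP 5.1) does not help, since an unobserved DLT is absent from that run too.

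**Conclusion.** The point holds in limited form. The SAP rule, as written, treats an unknown first-cycle outcome as a known non-DLT for patients lost after Day 15. In a small cohort with one DLT, a single such patient can decide whether a dose meets the 0.25 limit: clearly at 20 mg, narrowly at 160 mg, and at 320 mg with 1/4 against 1/3. In other constellations, including 40 mg and 80 mg as the current dose, it cannot.

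It would be tempting to conclude that the trial's MTD is wrong or understates toxicity. The documents do not support this: they give no observed DLT counts and do not say whether any patient left observation in the relevant interval. The number may be zero, in which case nothing changes. The sizes above rest on assumed cohort results and on the excluded patient not being replaced.

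**What to change.** 1. In SAP 5.1 and 6.3, define a patient as evaluable for the MTD if there is a DLT in the MTD evaluation period, or if at least two administrations were given and the patient was observed through the protocol's 28-day first cycle without a DLT.
2. State that this reads the one-cycle gloss in protocol 3.3.4.1 together with 3.1 and 4.1.3, and reconcile those passages.
3. Reconcile SAP 5.1 with Table 6.1:1 on where the window ends when no third infusion is given.
4. Report the model with and without incompletely observed patients, and add days observed to the listing in SAP 7.4.

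The cost is a few SAP edits and one extra model run. The downside is possibly one or two fewer patients in the MTD evaluation set and a slight upward pull on the estimated DLT rate; reporting both runs shows how large that is.

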5.2 SECONDARY ENDPOINTS

5.2.1 Key secondary endpoints

No key secondary endpoints are defined in this study.

5.2.2 Secondary endpoints

The secondary endpoints in Phase I are

- RBC Transfusion Independence (RBC TI)
- Hematologic improvement neutrophils (HI-N)
- Hematologic improvement platelets (HI-P)
- Hematologic improvement erythroid (HI-E)
- Time to HI-E response
- Mean hemoglobin increase ≥ 1.5 g/dL
- Duration of Response (RBC Transfusion Independence, HI-N, HI-P, HI-E or Objective Response)
- Overall Objective Response (OR) [Complete Response (CR), Partial Response (PR), and Hematologic Improvement (HI)]

RBC Transfusion Independence (RBC-TI):

The definition of RBC TI is given in section 5.1.2.3 of the CTP. RBC-TI is evaluated in patients who are transfusion dependent at baseline. Percentages will be calculated using all treated patients, who are transfusion dependent at baseline, as the denominator.

The investigator's assessment as reported on the "Disease Assessment eCRF" will be used for the analysis of this endpoint. No derivation from the "Concomitant Blood Product Therapies eCRF" is planned. Consistency between these two eCRF pages will be reviewed during the trial's Medical Quality Review Meetings (MQRMs).

HI-N, HI-P and HI-E:

HI-N, HI-P and HI-E are defined in section 5.1.2.3 of the CTP. The investigator's assessment as reported on the "Disease Assessment eCRF" will be used for the analysis of these endpoints. No derivation from the "Laboratory eCRF" (or the "Concomitant Blood Product Therapies eCRF") is planned. Consistency between these eCRF pages will be reviewed during the trial's Medical Quality Review Meetings (MQRMs).

Time to HI-E response:

Time to HI-E response is defined only for patients who achieve a HI-E response as follows:

Time to HI-E response [days] = date of first assessment indicating HI-E response – date of first administration of trial medication + 1.

Mean hemoglobin increase ≥ 1.5 g/dL:

The definition of "Mean hemoglobin increase ≥ 1.5 g/dL" is given in CTP section 5.1.2.3.

Duration of Response:

Duration of objective response is defined only for patients who achieve an overall response of CR or mCR or RBC TI.

Duration of response is defined as:

Duration of Response [days] = date of outcome – date of first assessment indicating CR or mCR or RBC TI after first administration of trial medication + 1.

The censoring rules and dates of outcome (i.e. event or censoring) for Duration of Response under different scenarios are specified in Table 5.2.2:1. The evaluation period for duration of response is until treatment discontinuation (see also section 5.1.2.3 of the CTP).

Table 5.2.2:1 Derivation rules for Duration of Response

| Situation | Outcome (event or censored) | Date of outcome |
|---|------------------------------------|---|
| No relapse, no death | censored | Date of last disease assessment |
| Relapse (no subsequent anti-cancer therapy before relapse) | event | Date of disease assessment of relapse |
| Death without relapse, no subsequent anti-cancer therapy | censored | Date of death |
| Death without relapse, but subsequent anti-cancer therapy prior death | censored | Date of last disease assessment before initiation of subsequent anti-cancer therapy |
| Subsequent anti-cancer therapy before relapse (check interval between start of new medication and relapse) | | |
| Interval ≤ 7 days | Event | Date of disease assessment of relapse |
| Interval > 7 days | Censored | Date of last disease assessment before initiation of subsequent anti-cancer therapy |

Overall Objective Response:

Overall Objective Response is defined as Complete Response (CR), Partial Response (PR), HI-N, HI-P, or HI-E. A patient's "Overall Objective Response" = "Yes" if one of these responses was reported at least once throughout the trial.

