**FU:** Follow-up starts 4 weeks after the EOT visit; Phase I patients: visits or telephone calls will occur at least every 4 weeks for 6 months. After the 6th follow-up visit, the patient will be considered off trial. Phase II patients: visits or telephone calls will occur at least every 4 weeks until 12 months after the last administration of BI 836858, after which these visits will occur every 6 months until the end of the trial. After implementation of CTP version 5.0, no further follow-up visits after EoR, unless follow-up is for S(AE) that occurred before EoR period.

\* The planned duration of a treatment cycle is 28 days; there will be two administrations of BI 836858 per cycle, on Days 1 and 15. All assessments should be performed prior to dose administration on dosing days, unless otherwise specified.

\*\* These visits are only for those patients who have received BI 836858 that are non-PD and equivocal as to if clinical benefit has been established, per investigator judgment, after 4 Cycles; up to 2 additional introduction cycles allowed prior to end of introduction treatment.

- 1 Visit window of +1 day only allowed beginning in Cycle 3 and for all subsequent cycles. In Cycles 1 and 2 visit window not allowed
- 2 Review of inclusion/exclusion criteria during screening and again on day of first administration.
- 3 After informed consent and review of inclusion/exclusion criteria (timing described in footnote 2). For phase II, randomization should be performed as close to the first treatment dose as possible. It may be performed on the day of the first administration (Cycle 1 day 1) prior to patient treatment, but no later than 21 days after patient signs informed consent.
- 4 For details refer to [Section 5.2.3.1](#). Urine has to be measured only at screening, EOC4 and EOT. Safety laboratory assessments may be completed up to 2 days prior to administration, or BSC treatment on trial (Phase II). An additional safety lab will be collected on day 2 (i.e., 24 hours after the first administration of BI 836858) and 24 hours after the first higher dose for patients who participate in intra-patient dose escalation. Other lab tests to be included: haptoglobin, direct Coombs test, and bilirubin (direct and indirect).

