## 5.1.2 Assessment of efficacy

### 5.1.2.1 Bone marrow aspirate and peripheral blood

Response will be assessed in bone marrow (BM), peripheral blood and clinically as specified in the [Flow Chart](#).

The investigator's overall assessment of the disease and confirmation of non-PD/non-relapse status will be required for the decision to continue with the next cycle of study treatment.

At baseline a BM aspirate is required. A BM biopsy will be required if aspiration is inadequate. During response assessment after treatment initiation, a BM aspirate will be sufficient and no BM biopsy will be required unless the aspirate results in a *punctio sicca* (dry tap) in which case a BM biopsy will be performed. The first scheduled bone marrow sample for response assessment will be performed at the end of Cycle 4. The BM aspirate (or biopsy if aspirate is inadequate) will be scheduled for response assessment at the EOC4 and at the time of disease progression/relapse or EOT, whichever occurs first. The classification of response is defined in Section 5.1.2.3.

An unscheduled BM examination should be performed as soon as possible when progression or relapse of MDS is suspected (based on clinical or laboratory findings) irrespective of the next scheduled BM assessment.

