### Duration of Response

- Response duration analysis is defined only for patients who achieve CR or mCR or RBC Transfusion Independency and is measured from the first date of achieving a response until the date of relapse. The date of relapse will be the earliest of the dates of the disease assessment (blood sample, bone marrow sample, or clinical assessment) in which the relapse was observed. For patients who die or are lost to follow-up without documented relapse, response duration will be censored, respectively, on the date of death, regardless of cause, or on the date of last disease assessment for the patients who are alive when lost to follow-up.

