### 6.2.2.3 End of Cycle 4 (EOC4)

This visit includes an evaluation for further treatment. Those patients with clinical benefit, CR or PR and who are tolerating the infusions well may continue until PD or other criteria for withdrawal are met as noted in [Section 3.3.4.1](#). For those patients who have received 8 administrations, this visit is to be performed 14 days ( $\pm 2$  days) after the 8th administration of BI 836858. For those patients who have received  $< 8$  administrations, who are still in remission, this visit is to be performed 4 months ( $\pm 2$  days) after Cycle 1 Visit 1. Phase II: For patients randomized to BSC, this visit to be completed 4 months ( $\pm 2$  days) after Cycle 1 Visit 1.

The following parameters and investigations will be obtained and /or performed:

- Safety lab parameters and urine analysis as specified in [Section 5.2.3.1](#)
  - Physical examination, weight and ECOG performance score
  - Vital signs at time points specified in [Section 5.2.5.1](#)
  - Serum pregnancy test in women of childbearing potential
  - 12-lead ECG
  - Adverse events (AEs)
  - Changes in concomitant therapies
  - Bone marrow aspiration
  - Molecular genetics and cytogenetics of MDS (Phase II patients only)
  - Number of transfusions
- 
- Clinical disease assessment - Eligibility for further administration may be performed up to 2 days prior to this visit

Phase II: For patients that are randomized to Arm B (BSC), following disease assessment confirmation at this visit, if patients have not progressed to high-risk MDS or AML, there is the opportunity to cross-in and receive BI 836858 study drug, providing they fulfil all inclusion/exclusion criteria. Alternatively, these patients may continue on in the Maintenance Cycles receiving BSC treatment until PD or other criteria for withdrawal are met.

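### SAP 5.2.2 dates HI-E and the start of Duration of Response by the first assessment showing the response, first scheduled at about Day 113, not by when the response was achieved

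*SAP*

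**What the plan says.** SAP 5.2.2 defines Time to HI-E as "date of first assessment indicating HI-E response – date of first administration of trial medication + 1". It starts Duration of Response at the "date of first assessment indicating CR or mCR or RBC TI after first administration of trial medication" and counts to the date of outcome, plus 1. The yes/no responses come from the investigator's entry on the Disease Assessment eCRF. SAP 5.2.2 plans no derivation of them from the laboratory or blood-product pages.

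Protocol 5.1.2.3 says that response duration "is measured from the first date of achieving a response until the date of relapse". SAP 4.1 and 4.2 list one clarification (the DLT endpoint) and one change (no Phase II analyses), but not this different start date.

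On timing, Protocol 5.1.2.1 states: "The first scheduled bone marrow sample for response assessment will be performed at the end of Cycle 4". The visit lists for Cycles 1 to 4 (Protocol 6.2.2.1 and 6.2.2.2) contain safety laboratory tests and transfusion counts but no disease assessment. Flow Chart 1 and Protocol 6.2.2.3 place the first clinical disease assessment at End of Cycle 4 (EOC4). Further ones follow in Cycles 5 and 6 and in maintenance.

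SAP Table 5.2.2:1 dates relapse by the disease assessment at which it is found and censors patients without relapse at their last disease assessment. SAP 7.5.2 provides listings only for both endpoints.

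**The concern.** RBC transfusion independence (RBC TI) needs at least 56 consecutive days without transfusion, and HI-E needs an improvement lasting at least eight weeks. Both can be complete about eight weeks before the first scheduled response assessment. If the clock is read at that assessment, Time to HI-E reflects the visit schedule more than the drug, and Duration of Response leaves out much or all of the transfusion-free time that made the patient a responder. Even a correct yes/no response would then carry uninformative dates. The listing is the only planned output for these endpoints, so its dates are the reported result.

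**Working it through.** Inputs:
- Dosing in the introduction cycles: "there will be two administrations of BI 836858 per cycle, on Days 1 and 15" of a 28-day cycle (notes to Flow Chart 1).
- EOC4: 14 days (±2) after the eighth administration, or 4 months (±2 days) after Cycle 1 Visit 1 for patients with fewer than eight (Protocol 6.2.2.3). Flow Chart 1 shows Day 28 ± 2 of Cycle 4.
- RBC TI and HI-E criteria: 56 days and eight weeks (Protocol 5.1.2.3).
- Maintenance Cycle 1 Visit 1 can fall within 7 days of EOC4 (Protocol 6.2.2.5).
- The two SAP 5.2.2 formulas, both of the form end − start + 1.

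1. **Day of EOC4.** The eighth administration is on Day 1 + 7 × 14 = 99. EOC4 is on Day 99 + 14 = 113, window 111 to 115. By the flow chart it is 3 × 28 + 28 = Day 112, window 110 to 114. The two routes agree within their windows. With fewer than eight administrations, 4 months is 4 × 365.25 / 12 ≈ 122 days, so about Day 123 (121 to 125).

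2. **Time to HI-E, if first recorded at EOC4.** 113 − 1 + 1 = 113 days. Eight weeks counted from Day 1 end on Day 56, so HI-E can be established from Day 57. A spread of up to 113 − 57 = 56 days between patients is reduced to one value.

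3. **Start of RBC TI duration, if first recorded at EOC4.** The earliest run begins on Day 1 and completes 56 days on Day 56. The SAP start is late by up to 113 − 56 = 57 days counted from completion, or 113 − 1 = 112 days counted from the first day of the run.

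4. **Example.** A patient is transfusion-free from Day 5 to Day 119, a run of 119 − 5 + 1 = 115 days, and completes 56 days on Day 60. Relapse is assessed on Day 120, seven days after EOC4.
   - SAP start: 120 − 113 + 1 = 8 days.
   - Start at completion of the 56 days: 120 − 60 + 1 = 61 days.
   - Start on the first day of the run: 120 − 5 + 1 = 116 days.

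5. **Censoring.** After protocol version 5.0, clinical disease assessments from Cycle 5 on are not mandatory, and findings enter the eCRF only if they qualify as an (S)AE (Flow Chart 1, footnote 20; Flow Chart 2, footnote 12). If EOC4 is the last recorded assessment, an ongoing responder is censored at 113 − 113 + 1 = 1 day.

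6. **Can the result be negative?** Take a run from Day 1 to Day 56 and a relapse dated to a Day 71 blood sample, with the response first recorded at EOC4: 71 − 113 + 1 = −41 days. This needs a relapse date earlier than the first recorded response assessment. If both dates are disease assessments taken in order, the minimum is 1 day.

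**The case against.** The strongest reply is that Day 113 is not certain for any individual. Protocol 5.1.2.1 says response is assessed in marrow, in peripheral blood and clinically, and requires an investigator's disease assessment before each next cycle. For relapse, Protocol 5.1.2.3 counts a blood sample as a disease assessment. The Disease Assessment eCRF is not in the documents, so its date field could hold a visit date, a sample date or an onset date. This stands as a condition on the figures. It does not remove the problem: the check before each cycle is described as confirming no progression or relapse, not as a response assessment, and the SAP formula does not ask for an onset date.

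Four stronger readings are tempting, and the documents do not support them:
- That EOC4 is the only scheduled assessment. It is the first; others follow in Cycles 5 and 6 and in maintenance, and suspected relapse prompts an unscheduled marrow examination.
- That Time to HI-E starts at the assessment. It starts at first administration and ends there.
- That negative durations follow from the SAP. Table 5.2.2:1 uses the assessment of relapse, so a negative value needs the condition in step 6.
- That a duration below 56 days contradicts the definition, or that the delay is simply 112 days. If a response is achieved only once the 56 days are complete, the qualifying period comes before the start, a short duration is no contradiction, and the largest delay is 57 days.

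It is also fair to say that these are secondary listings in a small Phase I trial whose recruitment was stopped, and that deriving dates from other pages goes beyond what the SAP planned. That limits the importance of the point but does not make the listed dates informative.

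**Conclusion.** The point holds in a conditional form. The SAP start of Duration of Response differs from the protocol's and is not declared as a change. If EOC4 is the first recorded response assessment and its date is the one used, HI-E times cluster near 113 days. RBC TI durations for early responders then begin 57 or 112 days late at the extreme, depending on how achieving the response is read. On either reading the example patient's 8 days is far too short (61 or 116 days). A 1-day censored duration is possible where later assessments were dropped after version 5.0.

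The consequence is limited to two secondary endpoints, listed only, among responders in 27 Phase I patients (21 escalation, 6 expansion). The primary MTD and DLT analyses are unaffected.

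**What to change.** In SAP 5.2.2, keep the investigator's yes/no response and change the dates:
- **RBC TI onset:** take it from the qualifying run of at least 56 transfusion-free days in the Concomitant Blood Product Therapies eCRF. State one convention, either the first day of the run or the day the 56 days are complete, consistent with Protocol 5.1.2.3.
- **RBC TI end:** the next RBC transfusion, or censoring at the last date with transfusion data recorded.
- **HI-E:** date it by the same convention from the haemoglobin and transfusion records.
- **CR and mCR, and any responder without a qualifying derived run:** keep the assessment date.
- List the assessment-date version alongside, and record the change in SAP Section 4.

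The cost is a little programming for the responders among 27 patients. Two limits remain. Laboratory-based HI-E dates are only as fine as the visit schedule: from Cycle 3, patients attend only for infusions unless medically indicated. Transfusion counts and laboratory tests in later cycles are also not mandatory after version 5.0, so some ongoing responders will still be censored early.
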